9	Interaction of breastfeeding and early vs. late postpartum (breastfeeding/ \leq 14 weeks; breastfeeding/ $>$ 14 weeks; no breastfeeding/ \leq 14 weeks; no breastfeeding/ $>$ 14 weeks [referent])	Uterine perforation

^a Secondary objectives include dichotomization of “early” and “late” postpartum categories. Separate propensity score models will not be *developed* for these objectives. Rather, the propensity scores calculated with the four-category variable will be used, and the distribution of scores will be collapsed into the categories for each secondary objective. Assessment of distributions of propensity scores will be performed within these collapsed categories.

Propensity scores for dichotomous exposure variables will be estimated by fitting a logistic regression model that incorporates data source (i.e., KPNC, KPSC, KPWA, or RI) and measured potential predictors of exposure as independent variables (all baseline variables in Section 9.3.1 will be considered). The dependent variable in the propensity score model is exposure status (e.g., women breastfeeding at the time of IUD insertion vs. not breastfeeding at the time of IUD insertion).

Propensity scores for the categorical variable (i.e., timing of postpartum insertion) will be estimated by fitting a multinomial logistic regression model that incorporates data source (i.e., KPNC, KPSC, KPWA, or RI) and measured potential predictors of exposure as independent variables (all baseline variables in Section 9.3.1 will be considered). The dependent variable in the propensity score model is exposure category (i.e., ≤ 6 weeks postpartum; > 6 and ≤ 14 weeks postpartum; > 14 and ≤ 52 weeks postpartum; > 52 weeks postpartum [referent]).

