^{*} Overlap weighting was chosen due to the versatility of the methodology. While the method has been subject to simulations and has been used in practice, further testing is underway. If concerns about this methodology arise due to articles published while this study is underway, then inverse probability treatment weighting (IPTW) will be used as the weighting method. If this occurs, IUD insertions will be excluded when there are no comparable patients in one group versus the other (i.e., nonoverlapping propensity scores in the upper and lower tails of the propensity score distribution); patients with propensity scores close to that boundary will be excluded from further analysis. Weighting will then be based on the inverse probability of treatment, and extreme weights (e.g., $> 10^4$) will be excluded (Kurth et al., 2006; Sturmer et al., 2010). This process is called “trimming” and may affect one group more than the other. From the weighted analysis, the average treatment effect within each exposure group will be obtained (Austin, 2013; Austin, 2014). If the exposed and unexposed groups are unbalanced after trimming and application of IPTW, then the logistic regression model will be revised by including interaction terms or higher order terms, and the covariate balance between the two groups will be re-evaluated based on the revised model (Austin, 2011; Rosenbaum and Rubin, 1984).

including interaction terms (e.g., with data source), higher order terms, or transformation of variables, and the covariate balance between the groups overall and within each data source will be re-evaluated based on the revised model (Austin, 2011; Rosenbaum and Rubin, 1984). When satisfactory balance between the exposed and unexposed groups is achieved (e.g., standardized difference < 0.1), the weighting will be incorporated in modeling for confounder-adjusted outcome assessments (Section 9.7.1.3.3). If satisfactory balance is difficult to achieve, especially if there are disparate allocation percentages between groups, matching of patients between groups may be considered.

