The balance across exposure groups will be assessed before and after weighting. The distribution of each variable will be compared between categories of the exposure variable, and balance parameters (i.e., standardized differences) (Austin and Stuart, 2015) will be calculated. Pairwise balance parameters (e.g., pairwise standardized differences) will be used for the categorical exposure variable in which each category will be compared to the referent group (> 52 weeks postpartum for postpartum period). The maximum of the pairwise standardized differences will also be reported. The balance between exposure groups will be assessed overall and within each data source. If the groups are unbalanced on key covariates after application of overlap weighting, then the logistic regression model will be revised by including interaction terms (e.g., with data source), higher order terms, or transformation of variables, and the covariate balance between the groups overall and within each data source will be re-evaluated based on the revised model. When satisfactory balance between the exposed and unexposed groups is achieved, the weighting will be incorporated in modeling for confounder-adjusted outcome assessments (Section 4.1.5). The exposure groups are considered balanced if the standardized difference is less than 0.20 (generally considered small) (McCaffrey et al., 2013). If satisfactory balance is difficult to achieve, which is not expected for overlap weighting, matching of patients between groups may be considered.

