Concomitant gynecological procedure	Indicator variable: 1 = Yes if any of the following procedures occurred on the index date: abortion, aspiration and curettage, dilation and curettage, excision/biopsy of cervix or uterus, ablation, colposcopy and other cervical procedures, hysteroscopy, laminaria, laparoscopy, lysis adhesions, myomectomy, nerve procedure, salpingectomy/oophorectomy 0 = No if none of the above procedures occurred on the index date
Exposures	
Postpartum number of days	Number of person-days, starting on the most recent pregnancy delivery date prior to or on the index date and ending on the index date . There will be a derived postpartum number of days associated with each insertion for each woman. This variable will range from 0 to 365 days and will be missing if the most recent pregnancy delivery date is not recorded or is more than 365 days before the index date .
Postpartum—14-week, dichotomous	Indicator variable: * If postpartum number of days ≤ 98, then postpartum—14-week, dichotomous = 1 * If postpartum number of days > 98 or missing, then postpartum—14-week, dichotomous = 0

Variable	Definition ^a
Postpartum—36-week, dichotomous	Indicator variable: * If postpartum number of days ≤ 252 , then postpartum—36-week, dichotomous = 1 * If postpartum number of days > 252 or missing, then postpartum—36-week, dichotomous = 0
Postpartum—categorical	Categorical variable: * If postpartum number of days ≤ 42 , then postpartum—categorical = 1 (6 weeks or less) * If postpartum number of days > 42 and ≤ 98 , then postpartum—categorical = 2 (> 6 to ≤ 14 weeks) * If postpartum number of days > 98 and ≤ 365 , then postpartum—categorical = 3 (> 14 to ≤ 52 weeks) * If postpartum number of days > 365 or missing, then postpartum—categorical = 0 (> 52 weeks or no delivery)
Outcomes	
Person-time at risk (days, i.e., time to event/censor)	Number of person-days, starting on the index date of IUD insertion and ending on the earliest of date uterine perforation confirmed , date IUD expulsion confirmed , or censoring date . A derived number for person-time at risk will be associated with each IUD insertion for each woman.
Uterine perforation event indicator	Indicator variable: 0 = No date of uterine perforation confirmed during the person-time at risk 1 = Yes, date of uterine perforation confirmed during the person-time at risk

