6.2.2.2 Comparing Adjusted Hazard Ratios Among First Observed IUD Insertions

Adjusted hazard ratios associated with the first observed IUD insertions will be estimated for secondary objectives 14-16, and 19 using the same analysis approach (i.e., overlap weighting) as described in Section 6.2.1, with the following exceptions.

1. For type of IUD, analyses may be conducted by data source. However, due to data source restrictions, any results on type of IUD by data source will not be reported.
2. For secondary objectives that include dichotomization of “early” and “late” postpartum categories, separate propensity score models will not be developed. Rather, the propensity score model developed for the four-category variable will be used. The propensity score for dichotomous exposed group will be calculated by collapsing multiple categories (e.g., propensity score for ≤ 14 weeks = propensity score for ≤ 6 weeks + propensity score for > 6 to ≤ 14 weeks).
3. The analyses for objective 19 (menorrhagia) will be performed only if more than 20,000 IUD insertions with an indication of menorrhagia can be included in the analysis.

Balance will be assessed between exposure groups prior to and after weighting. Crude hazard ratios will also be reported.

The same set of analysis tables and figures as those created for objective 1 will be generated, except that no sensitivity analyses will be conducted for these secondary objectives.

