9.3 Propensity Score Models Defined by Exposure and Outcomes of Interest

Model Number	Exposure (Dependent Variable of Propensity Score Model)	Outcome (Not Included in Propensity Score Model)	IUD Insertion	Covariate Selection	Objective Number
1	Breastfeeding status (yes vs. no)	Uterine perforation	First insertion	Yes	1 (primary objective) 29
2	Postpartum insertion (4 categories)	Uterine perforation	First insertion	Yes	2 (primary objective) 14 ^a 15 ^a 17 ^a 31
3	IUD type (LNG vs. copper)	Uterine perforation	First insertion	Yes	16
4	Menorrhagia (yes vs. no)	Uterine perforation	First insertion	Yes	19
5	Breastfeeding status (yes vs. no)	IUD expulsion	First insertion	Yes	20 30
6	Postpartum insertion (4 categories)	IUD expulsion	First insertion	Yes	23 21 ^a 22 ^a 25 ^a 32
7	IUD type (LNG vs. copper)	IUD expulsion	First insertion	Yes	24
8	Menorrhagia (yes vs. no)	IUD expulsion	First insertion	Yes	27
9	Interaction of breastfeeding and early vs. late postpartum (breastfeeding/ \leq 14 weeks; breastfeeding/ $>$ 14 weeks; no breastfeeding/ \leq 14 weeks; no breastfeeding/ $>$ 14 weeks [referent])	Uterine perforation	First insertion	Yes	28
10	Breastfeeding status (yes vs. no)	Uterine perforation	Subsequent insertions	No ^b	18
11	Postpartum insertion (4 categories)	Uterine perforation	Subsequent insertions	No ^b	18 ^a
12	IUD type (LNG vs. copper)	Uterine perforation	Subsequent insertions	No ^b	18
13	Breastfeeding status	IUD expulsion	Subsequent insertions	No ^b	26
14	Postpartum insertion (4 categories)	IUD expulsion	Subsequent insertions	No ^b	26 ^a
15	IUD type (LNG vs. copper)	IUD expulsion	Subsequent insertions	No ^b	26

IUD = intrauterine device; LNG = levonorgestrel.

- ^a Secondary objectives include dichotomization of “early” and “late” postpartum categories. Separate propensity score models will not be *developed* for these objectives. Rather, the propensity scores calculated with the four-category variable will be used. The propensity scores for dichotomous exposure groups will be calculated by collapsing multiple categories (e.g., propensity score for ≤ 14 weeks = propensity score for ≤ 6 weeks + propensity score for > 6 to ≤ 14 weeks).

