Objectives 20 through 27^{c,d}	Comparative analysis for IUD expulsion		Same set of tables and figures as objectives 1, 2, 14-19, excluding Tables 1.4 and 2.4 (106 tables + 47 figures)
Objective 28	Effect modification		
Table 28.1	Effect modification of breastfeeding status and postpartum status on uterine perforation	Layout 11	Pooled (1 table)
Objective 29	Effect modification		
Table 29.1	Effect modification of IUD type on breast feeding status and uterine perforation	Layout 12.1	Pooled (1 table)
Objective 30	Effect modification		
Table 30.1	Effect modification of IUD type on breast feeding status and IUD expulsion	Layout 12.1	Pooled (1 table)
Objective 31	Effect modification		
Table 31.1	Effect modification of IUD type on postpartum status and uterine perforation	Layout 12.2	Pooled (1 table)
Objective 32	Effect modification		
Table 32.1	Effect modification of IUD type on postpartum status and IUD expulsion	Layout 12.2	Pooled (1 table)
Development of propensity score models			
Tables 33.1.1 through 33.1.2	Assessing relationship with outcome: crude HR for baseline covariates	Layout 4	Pooled (2 tables)
Tables 33.2.1 through 33.2.9	Assessing confounding effect: HR adjusted for one covariate	Layout 5	Pooled (9 tables)
Tables 33.3.1 through 33.3.15	Propensity score model	Layout 6	Pooled (15 tables)
Figure 33.1.1 through 33.1.15	Histograms with kernel smoothing of propensity scores by exposure		Pooled (15 figures)
Impact of transition from ICD-9-CM to ICD-10-CM			
Tables 34.1	Percentage of uterine perforation or IUD expulsion prior to and after implementation of ICD-10-CM coding	Layout 13	Pooled and by site (1 table)

HR = hazard ratio; ICD-9-CM = *International Classification of Diseases, 9th Revision, Clinical Modification*; ICD-10,CM = *International Classification of Diseases, 10th Revision, Clinical Modification*; IUD = intrauterine device.

Note: In the report, analysis tables related to IUD type will report only the results across all sites, not by site. However, by-site analyses may be conducted for internal purposes and will not be shared with Bayer.

^a Table layouts are included in Section 9.5.

- ^b If breastfeeding status, postpartum timing, or IUD type are not included within a propensity score (as independent variables when not the dependent variable), then a separate Cox model also including these variables as covariates will be developed. If this occurs additional tables will be added using Table Layout 7.

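### The score for ≤ 36 vs > 36 weeks postpartum cannot be built by collapsing the four-category propensity model, because day 252 lies inside the > 14 to ≤ 52 week category

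*SAP*

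**What the plan says.** SAP Section 4.6, Table 1, derives two postpartum variables that matter here. The four-level variable breaks at days 42, 98 and 365, and its third level is a single block: "If postpartum number of days > 98 and ≤ 365 , then postpartum—categorical = 3". The 36-week variable breaks at day 252: at or below that day, "then postpartum—36-week, dichotomous = 1".

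SAP Section 6.2.2.2, item 2, rules out separate propensity models for the early/late dichotomies and reuses the four-category model: "The propensity score for dichotomous exposed group will be calculated by collapsing multiple categories". Section 9.3, footnote a, repeats the rule ("The propensity scores for dichotomous exposure groups will be calculated by collapsing multiple categories"). The only worked example in either place is the 14-week one, where the scores for ≤ 6 weeks and > 6 to ≤ 14 weeks are added. Protocol Section 9.7.1.3.2, Table 6 footnote a, has the same approach: "the distribution of scores will be collapsed into the categories for each secondary objective".

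Footnote a in SAP 9.3 is attached to objectives 14, 15 and 17 (model 2), to 21, 22 and 25 (model 6), and to the postpartum models for subsequent insertions in 18 and 26 (models 11 and 14). Of these, 15, 17, 22 and 25 use the 36-week cut. Objectives 18 and 26 repeat 15 and 22 in subsequent insertions. The adjusted IRR and IRD (SAP 4.1.8 and 4.1.10) take their weights from the same propensity models as the hazard ratios.

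**The concern.** Collapsing means adding the probabilities of whole categories. For that to give the score of a dichotomous exposure, the dichotomy must cut at a category boundary. The 14-week cut does; the 36-week cut does not. A programmer who follows the SAP has no defined score for the 36-week contrast and must choose among the ≤ 14-week sum, the ≤ 52-week sum, or an unplanned pro-rating of the third category. These give different weights and different adjusted estimates, and the choice would be made after data access by analysts who, under SAP 4.1.5, are not blinded to outcome.

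The SAP prefers overlap weights partly because they balance covariate means exactly. That property holds only when the score is the probability of the exposure being compared; otherwise residual imbalance passes into the adjusted HR, IRR and IRD. Objectives 15 and 17 are the planned comparison with EURAS-IUD, the study behind the postmarketing requirement.

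**Working it through.** **1. Cut points.** 14 × 7 = 98 and 36 × 7 = 252, which reproduces SAP Table 1. The four categories are days 0–42, 43–98, 99–365, and > 365 or no recorded delivery. Checking every union of these categories:
- days 0–98 equal categories 1 + 2, so the 14-week collapse is valid;
- days 0–252 equal no union. Category 3 has 154 days at or below day 252 and 113 above it.

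Writing e1, e2, e3 for the fitted probabilities of the first three categories, e1 + e2 is the score for ≤ 14 weeks and e1 + e2 + e3 the score for ≤ 52 weeks. Neither is P(≤ 36 weeks | X). This step needs no assumption.

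**2. Why a substitute score loses balance.** Let E(x) and U(x) be the masses of exposed (≤ 36 weeks) and unexposed women at covariate value x. SAP 4.1.5 weights the exposed by 1 − e(x) and the unexposed by e(x), giving weighted masses E(x)(1 − e(x)) and U(x)e(x). If e = E/(E + U), both equal EU/(E + U) at every x and balance is exact. For any other e the ratio E(1 − e)/(Ue) in general varies with x, and imbalance remains. Pro-rating, e1 + e2 + s·e3 with s the share of category 3 at ≤ 36 weeks, is exact only if that share is unrelated to the covariates.

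**3. How many women.** From Protocol 9.5, 225,000 first insertions at 5:20:5:70:
- category 3: 0.05 × 225,000 = 11,250;
- ≤ 36-week group: between 0.25 × 225,000 = 56,250 and 0.30 × 225,000 = 67,500, as the split of category 3 is not given;
- category 3 women as a share of that group: between 0 and 11,250/67,500 = 16.7%.

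**4. Illustrative size (assumed inputs).** One binary covariate; prevalence 0.20, 0.25 or 0.30 at > 52 weeks; seven values from 0.40 to 0.97 in each of four postpartum groups (≤ 6, > 6–14, > 14–36, > 36–52 weeks), varied independently; s at eight values from 0.2 to 0.9; allocation 5:20:5:70. That is 3 × 7⁴ × 8 = 57,624 scenarios. The measure is the absolute standardized difference after weighting, with the variance taken from the weighted prevalences.

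| Score used | Median | 90th percentile | Maximum | > 0.1 | > 0.20 |
|---|---|---|---|---|---|
| True P(≤ 36) | 0 | 0 | 0 | 0% | 0% |
| e1 + e2 | 0.056 | 0.163 | 0.478 | 27.3% | 4.9% |
| e1 + e2 + e3 | 0.041 | 0.135 | 0.439 | 19.3% | 2.0% |
| Pro-rated | 0.023 | 0.061 | 0.214 | 1.2% | < 0.1% |
| Unweighted | 0.936 | 1.611 | 2.494 | – | – |

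**5. Would the balance check catch it?** The SAP limit is 0.20 ("The exposure groups are considered balanced if the standardized difference is less than 0.20"), while the protocol's example is tighter ("When satisfactory balance between the exposed and unexposed groups is achieved (e.g., standardized difference < 0.1"). Of the scenarios above 0.1, (27.3 − 4.9)/27.3 = 82% and (19.3 − 2.0)/19.3 = 90% would pass at 0.20.

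**6. Second illustration.** A simulation of 225,000 insertions with two continuous covariates (assumed effects) gave largest standardized differences of 0.056 (e1 + e2) and 0.090 (e1 + e2 + e3) with category 3 near 5%, and 0.18 and 0.29 with category 3 near 15%. A binary model at day 252 gave 0.000 throughout.

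**The case against.** The case for a lower grade has four parts.

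- **Small effect at the planned allocation.** With category 3 near 5%, the simulation stayed below 0.1 for either sum. The grid's tails depend on letting neighbouring postpartum groups differ by up to 57 percentage points. If the four postpartum prevalences lie within 20 points of each other (8,184 scenarios), only 9% and 6% exceed 0.1, and 0.1% and 0% exceed 0.20. Taking the better-balancing sum in each scenario of the full grid, 2.3% exceed 0.1.
- **Visibility.** SAP 6.2.2.2 requires balance before and after weighting, and SAP 9.4 gives objective 15 the full set of balance tables, pooled and by site. A reader can apply 0.1 whatever the SAP limit is.
- **Another remedy exists.** Besides extra model terms, SAP 4.1.5 and the protocol allow matching to be considered.
- **Limited reach.** Only secondary objectives are touched, objective 15 is labelled a sensitivity analysis, and crude 36-week estimates are still reported.

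All of this is fair on degree, and the percentages in the grid are shares of assumed scenarios, not probabilities. None of it supplies the missing score. Extra terms in a four-category model cannot split category 3 at day 252. Matching is discretionary and would itself need a 36-week score if done on the propensity score. Picking whichever sum balances better is sensible, but the plan does not provide for it.

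**Conclusion.** The concern holds. The collapsing rule is valid for the 14-week cut and cannot be carried out for the 36-week cut, so the adjusted 36-week results in objectives 15, 17, 22 and 25, and in the matching parts of 18 and 26, cannot be weighted correctly as written. This rests only on the day limits in SAP Table 1.

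The numerical consequence is uncertain. It depends on how category 3 splits at day 252 and how covariates differ across that split, neither of which the documents give. If category 3 is about 5% of insertions, residual imbalance is likely to be modest in most settings, and a wrong score would usually still remove most of the unweighted imbalance. It grows if category 3 is larger or its two parts differ markedly. The primary objectives, the 14-week objectives (14 and 21) and all crude estimates are unaffected. It should be fixed before analysis because the correction is simple and the alternative is an unplanned choice among scores.

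**What to change.** For each outcome, fit a binary logistic propensity model with the 36-week indicator (≤ 252 days = 1) as dependent variable: one for objectives 15 and 17, one for 22 and 25, with matching subsequent-insertion models for the 36-week parts of 18 and 26. Alternatively, for these objectives only, fit a five-level multinomial model with category 3 split at day 252, so that the ≤ 36-week score is the sum of the first three probabilities. Leave the primary four-category model as it is, keep collapsing for the 14-week objectives, and state that it applies to that cut alone.

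Correct SAP 6.2.2.2 item 2, the model list and footnote a in SAP 9.3, and Protocol Table 6 footnote a. In SAP 9.4, extend "Tables 33.3.1 through 33.3.15" and the matching propensity score figures.

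The cost is one extra model beside each of models 2, 6, 11 and 14 (15 + 4 = 19). Covariate selection has to be repeated for the two first-insertion models, since the 10% change rule depends on the exposure; under SAP 4.1.5 the subsequent-insertion models inherit the selected terms. All covariates and day counts are already planned, so no new data are needed.

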9.4 List of Planned Analysis Tables and Figures

Table/Figure Number	Content	Table Layout ^a	Note
Population Characteristics			
Tables 0.1.1 through 0.1.5	Baseline characteristics overall, by uterine perforation and by IUD expulsion; complete patient population, first insertions	Layout 1	Pooled and by site (5 tables)
Tables 0.2.1 through 0.2.5	Baseline characteristics overall, by uterine perforation and by IUD expulsion; breastfeeding status available, first insertions	Layout 1	Pooled and by site (5 tables)
Tables 0.3.1 through 0.3.5	Baseline characteristics overall, by uterine perforation and by IUD expulsion; IUD type available, first insertions	Layout 1	Pooled and by site (5 tables)
Tables 0.4.1 through 0.4.5	Baseline characteristics overall, by uterine perforation and by IUD expulsion; complete patient population, subsequent insertions	Layout 1	Pooled and by site (5 tables)
Tables 0.5.1 through 0.5.5	Baseline characteristics overall, by uterine perforation and by IUD expulsion; breastfeeding status available, subsequent insertions	Layout 1	Pooled and by site (5 tables)
Tables 0.6.1 through 0.6.5	Baseline characteristics overall, by uterine perforation and by IUD expulsion; IUD type available, subsequent insertions	Layout 1	Pooled and by site (5 tables)
Objective 1	Breastfeeding and uterine perforation		
Table 1.1	Crude and adjusted HR for breast feeding status	Layout 2.1	Pooled and by site (1 table)
Tables 1.2.1 through 1.2.5	Baseline characteristics by exposure and absolute standardized difference	Layout 3.1	Pooled and by site (5 tables)
Tables 1.3.1 through 1.3.5	Baseline characteristics and absolute standardized differences after overlap weighting	Layout 3.1	Pooled and by site (5 tables)
Figure 1.1.1 through 1.1.5	Standardized differences in the unweighted and weighted samples		Pooled and by site (5 figures)
Table 1.4	Adjusted HR from Cox model with baseline covariates (sensitivity analysis)	Layout 7	Pooled, including interaction with site (1 table ^b)
Objective 2	Postpartum period and uterine perforation		
Tables 2.1	Crude and adjusted HR for postpartum status	Layout 2.2	Pooled and by site (1 table)
Tables 2.2.1 through 2.2.5	Baseline characteristics by exposure and absolute standardized difference	Layout 3.2	Pooled and by site (5 tables)
Tables 2.3.1 through 2.3.5	Baseline characteristics and absolute standardized differences after overlap weighting	Layout 3.2	Pooled and by site (5 tables)

Table/Figure Number	Content	Table Layout ^a	Note
Figure 2.1.1 through 2.1.5	Standardized differences in the unweighted and weighted samples		Pooled and by site (5 figures)
Table 2.4	Adjusted HR from Cox model with baseline covariates (sensitivity analysis)	Layout 7	Pooled, including interaction with site (1 table ^b)
Objectives 3 through 12	Crude incidence rate and cumulative incidence by analysis set, postpartum status, breastfeeding status, IUD type, menorrhagia		
Tables 3.1 through 3.5	Crude incidence rate and cumulative incidence	Layout 8	Pooled and by site (5 tables)
Figure 3.1	Kaplan-Meier cumulative incidence plot by analysis set		Pooled (1 figure)
Figure 4.1	Kaplan-Meier cumulative incidence plot by postpartum status		Pooled (1 figure)
Figure 5.1	Kaplan-Meier cumulative incidence plot by breastfeeding status		Pooled (1 figure)
Figure 6.1	Kaplan-Meier cumulative incidence plot by IUD type		Pooled (1 figure)
Figure 7.1	Kaplan-Meier cumulative incidence plot by menorrhagia		Pooled (1 figure)
Objectives 8 through 12	Crude incidence rates and cumulative incidence for IUD expulsion		Same set of tables and figures as objectives 3-7 (5 tables + 5 figures)
Objective 13			
Table 13.1 through 13.5	Prevalence of difficult IUD insertion by exposure and outcome	Layout 9	Pooled and by site (5 tables)
Objective 14	Postpartum period (≤ 14 vs. > 14 weeks) and uterine perforation		Same set of tables and figures as objective 1 excluding Table 1.4 (11 tables + 5 figures)
Objective 15	Postpartum period (≤ 36 vs. > 36 weeks) and uterine perforation		Same set of tables and figures as objective 1 excluding Table 1.4 (11 tables + 5 figures)
Objective 16	IUD type and uterine perforation		Same set of tables and figures as objective 1 excluding Table 1.4 Only pooled results will be reported (3 tables + 1 figures)
Objective 17	Postpartum period (≤ 36 vs. > 36 weeks) and uterine perforation		
Table 17.1	Crude and adjusted incidence rate ratios and differences for uterine perforation at 1 year and 5 years of follow-up	Layout 10	Pooled and by site (1 table)
Objective 18^c	Subsequent insertions for uterine perforation (subsequent insertions)		Same set of tables and figures as objectives 1, 2, 14, 15, 16 excluding Tables 1.4 and 2.4 (47 tables + 21 figures)
Objective 19^d	Menorrhagia and uterine perforation		Same set of tables and figures as objective 1 excluding Table 1.4 (11 tables + 5 figures)

Table/Figure Number	Content	Table Layout ^a	Note
Objectives 20 through 27^{c,d}	Comparative analysis for IUD expulsion		Same set of tables and figures as objectives 1, 2, 14-19, excluding Tables 1.4 and 2.4 (106 tables + 47 figures)
Objective 28	Effect modification		
Table 28.1	Effect modification of breastfeeding status and postpartum status on uterine perforation	Layout 11	Pooled (1 table)
Objective 29	Effect modification		
Table 29.1	Effect modification of IUD type on breast feeding status and uterine perforation	Layout 12.1	Pooled (1 table)
Objective 30	Effect modification		
Table 30.1	Effect modification of IUD type on breast feeding status and IUD expulsion	Layout 12.1	Pooled (1 table)
Objective 31	Effect modification		
Table 31.1	Effect modification of IUD type on postpartum status and uterine perforation	Layout 12.2	Pooled (1 table)
Objective 32	Effect modification		
Table 32.1	Effect modification of IUD type on postpartum status and IUD expulsion	Layout 12.2	Pooled (1 table)
Development of propensity score models			
Tables 33.1.1 through 33.1.2	Assessing relationship with outcome: crude HR for baseline covariates	Layout 4	Pooled (2 tables)
Tables 33.2.1 through 33.2.9	Assessing confounding effect: HR adjusted for one covariate	Layout 5	Pooled (9 tables)
Tables 33.3.1 through 33.3.15	Propensity score model	Layout 6	Pooled (15 tables)
Figure 33.1.1 through 33.1.15	Histograms with kernel smoothing of propensity scores by exposure		Pooled (15 figures)
Impact of transition from ICD-9-CM to ICD-10-CM			
Tables 34.1	Percentage of uterine perforation or IUD expulsion prior to and after implementation of ICD-10-CM coding	Layout 13	Pooled and by site (1 table)

HR = hazard ratio; ICD-9-CM = *International Classification of Diseases, 9th Revision, Clinical Modification*; ICD-10,CM = *International Classification of Diseases, 10th Revision, Clinical Modification*; IUD = intrauterine device.

Note: In the report, analysis tables related to IUD type will report only the results across all sites, not by site. However, by-site analyses may be conducted for internal purposes and will not be shared with Bayer.

^a Table layouts are included in Section 9.5.

- ^b If breastfeeding status, postpartum timing, or IUD type are not included within a propensity score (as independent variables when not the dependent variable), then a separate Cox model also including these variables as covariates will be developed. If this occurs additional tables will be added using Table Layout 7.
- ^c The analyses by site for objectives 18, and 26 will be done only for sites with more than 20,000 subsequent IUD insertions.
- ^d The analyses for objectives 19 and 27 will be done only if more than 20,000 IUD users with an indication of menorrhagia can be included in the analysis.

